**Figure 1 (repeat) - CaRISMA study design with two interventions arms and 12 months of follow-up for all participants.**

**1st Arm in Study Design: Computerized cognitive behavioral therapy (cCBT) for pain.** The cCBT program will teach users how to recognize negative thoughts and emotions, use cognitive skills and problem-solving, and apply coping behaviors such as distraction, activity scheduling, and relaxation. The cCBT arm emphasizes skills acquisition and learning through practice; thus, the program involves homework assignments and challenges, as well as continued check-ins with a health coach who helps reinforce the CBT skills and encourages practice and program engagement. The cCBT program also give users access to a study-associated Facebook page where they can discuss with other patients issues they faced and what skills were or could be used to address them. This intervention is consistent with the tailored behavioral services patients would receive individually or as a group when working with a psychologist or behavioral pain specialist.

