In the first three months of the study, intervention participants will complete all modules of their assigned study arm (cCBT or m-Education) at their own pace. The recommended progression is one module per week; this will give participants time to practice the techniques taught in each module. Participants will be asked to complete a daily electronic diary to track their pain symptoms.

Only intervention arm participants will receive follow up assessment. The convenience comparison group will not be followed with scheduled assessments.

**1st Follow-Up (T1).** At the end of month 3 (i.e., three months after enrollment, on the same date the participant began the study) participants will again receive a link to our online survey tool to complete the second iteration of Painimation, the SCSS, PROMIS, ASCQ-ME, PHQ-9, and GAD-7. If participants have questions while completing these questionnaires, they may contact their health coach for guidance. Participants will also be asked to complete daily pain intensity entries in the electronic diary. If participants do not complete the questionnaires or the pain intensity entries, health coaches will contact them and remind them to do so. The 48 patients selected for qualitative interviews will have their second interview with Qual-EASE at this time.

Between months 4-6, participants will continue to log their daily pain diary in the CaRISMA intervention but will no longer be expected to have weekly check-ins with their health coach.

**2nd Follow-Up (T2).** At the end of month 6, participants will receive a link to our online survey tool to complete Painimation, SCSES, PROMIS, ASCQ-ME, PHQ-9, and GAD-7 for the third time. Note: participants will not complete the COMM at T2. Though scheduled weekly check-ins with health coaches will have ceased, participants will still have the opportunity to contact their health coach as needed. Participants will continue to complete daily pain intensity entries through the electronic diary.

Between months 6-12, participants will continue daily pain diary submissions and communication with health coaches as needed. Additionally, Qual EASE will conduct the final set of qualitative interviews with the 48 randomly selected participants.

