### 6.3 MEASURES TO MINIMIZE BIAS: RANDOMIZATION AND BLINDING

**Randomization:** Participants will be randomized in an equal fashion (1:1) to both study arms. Random permuted block randomization will be used to create an allocation list that will be integrated within our Web-based data entry system. Stratification will be based on recruitment site (Pitt, Duke, Hopkins, OSU, UIC) or through one of the community partners (SC101, SCCC, and Sickle Cell Warriors).

**Reduce the potential for biases.** The introduction to both interventions will look identical and participants will not be told what type of training they are receiving. We will make every effort to mask the intervention type; however, as with all behavioral interventions, completely blinding participants to the intervention is challenging. The investigative team will continue to maintain clinical equipoise regarding the comparative therapeutic merits of each treatment. Randomization will avoid selection bias as well as volunteer or referral bias. A dropout analysis will be carried out to determine the contribution of attrition bias. All outcomes measures will be collected electronically, without an interview, to avoid expectation bias. We have also found this mode of data collection to be superior to assessments by phone for timely follow-up. Finally, we will avoid participant recall or memory bias by asking patients to record daily pain, fatigue, and other health outcomes via mobile device.

To limit potential bias from investigators, we are implementing a dual PI plan that separates data collection, monitoring, and analysis from the day-to-day implementation of the study interventions and engagements with community partners who can influence the outcomes of the trial. Broadly put, [name] will be primarily responsible for stakeholder and community engagement and the scientific/clinical aspects of this trial, while [name] will be responsible for the data and statistical analysis of the trial. In addition to limiting bias, we believe that due to the intensive plan we have outlined for stakeholder and community engagement, the overall project benefits from having a PI ([name]) who is dedicated to this role and who has less responsibility for data oversight.

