### 6.4 STUDY INTERVENTION/EXPERIMENTAL MANIPULATION ADHERENCE

The major assumption is that patients will complete the intervention program to which they are randomly assigned. Although we have implemented several methods to promote engagement and limit dropout (e.g., health coaches), digital interventions often experience high attrition over time with few participants completing all assigned modules. We will track the reasons for noncompletion and seek patterns (e.g., moved away, died, started working and became too busy, people with higher cognitive level lost interest) that are amenable to statistical analysis of the missing data.

We will have monthly study retention meetings led by [name] and [name] to discuss recruitment, retention, and engagement at all sites. The health coaches will report to [name] and the study PIs if they are having difficulty contacting any participant on the study. [name] will also visit the health coaches at the University of Pittsburgh and the study staff at each clinical site to teach them how to work effectively with this patient population. She will occasionally visit with the health coaches at the University of Pittsburgh for booster sessions.

[name] will train health coaches on how to keep track of each participant's progress throughout the intervention. Each participant will be required to complete all modules, as well as weekly health coach check-ins during the first 12 weeks, and daily pain diaries throughout the 12 months of the study. In addition, participants will also be required to complete Painimation, , the SCSES, PROMIS, ASCQ-ME, PHQ-9, and GAD-7 questionnaires at baseline, 3-, 6-, and 12-month time points, as well as the COMM at baseline and 12-month follow-up. Failure to complete any of these will prompt health coaches to reach out via text message or phone to encourage participants to complete missing items. The qualitative interview delivered by Qual EASE is the only optional activity in the intervention. Since only 48 of the 350 participants will be selected for interview, any participant that opts out will be replaced by another participant, of those not previously selected.

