### 7.3 LOST TO FOLLOW-UP

**Intervention engagement and health coach contacts.** Patients who stop reporting data in the intervention will receive inquiry text messages or a phone call (Health Coach Protocol). Since participation in the study is completely voluntary, patients may choose to discontinue the intervention at any time. During the first 12 weeks, participants are encouraged to have weekly check-ins with health coaches. This can be in the form of a text or email where there is at least one response from the participant, or phone call of any duration. Failure to check in with health coach will not affect enrollment in the study; however, health coaches will reach out three times to solicit a text, email, or phone call response from participants.

**Follow-up assessments.** The study sites will take preventive measures to avoid a subject's being lost to follow-up (e.g., document different ways of contact such as telephone number, email address, etc.). At baseline, 3-, 6-, and 12-month time points participants will receive links to complete Painimation, the SCSES, PROMIS, ASCQ-ME, PHQ-9, and GAD-7 on our online survey tool; COMM questionnaires will be sent at baseline and 12 months (See **Section 4.1 Overall Design for schedule breakdown**). Completion of the questionnaires is a required component of the study. Not completing questionnaires within 4 weeks of due date is considered a missed follow-up. In the event that a follow-up assessment is not completed, every possible effort will be made by study site personnel to contact the subject. For each follow-up, at least three documented contact attempts must be made on different days to the last available telephone number. If the subject is still unreachable after all contact attempts, they will be considered to be lost to follow-up (LTF). The site should document all attempts and LTF information in the trial database (see **Table 9**).

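### Participants may ask the coach who supports their assigned programme for guidance on the outcome questionnaires, and the documents set no limit on what the coach may say

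*Protocol*

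**What the plan says.** **Guidance.** Protocol section 4.1, in the paragraph on the first follow-up (T1, month 3), lists the online questionnaires, PROMIS Pain Interference, PHQ-9 and GAD-7 among them, and then says: "If participants have questions while completing these questionnaires, they may contact their health coach for guidance".

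**Reminders.** The same paragraph continues: "If participants do not complete the questionnaires or the pain intensity entries, health coaches will contact them and remind them to do so". Section 6.4 lists the modules, weekly check-ins, daily diaries and the questionnaires at baseline, 3, 6 and 12 months, and adds: "Failure to complete any of these will prompt health coaches to reach out via text message or phone to encourage participants to complete missing items".

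**Month 6.** The T2 paragraph of section 4.1 says that scheduled check-ins have stopped but the coach can still be contacted when needed. It does not repeat the sentence on questionnaire guidance.

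**Coach role.** Section 4.1 describes the coach in the cCBT arm as "a health coach who helps reinforce the CBT skills and encourages practice and program engagement". In m-Education, participants discuss the material with the coach.

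**Stated safeguard.** Section 6.3 says: "All outcomes measures will be collected electronically, without an interview, to avoid expectation bias". It also describes an attempt to mask participants to the type of training. Section 4.1 calls the trial open-label.

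**Endpoint.** The SAP's primary outcome is change in PROMIS Pain Interference at 6 months, a self-report measure.

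**The concern.** The person a participant may ask about an outcome item is the person who has supported them through one particular programme. A remark on what an item means, or what period or kind of interference to count, can move a self-reported score. If the adviser knows the arm and expects one programme to do better, the remark can lean that way. The SAP hypotheses do favour cCBT.

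Section 6.3 relies on the absence of an interviewer to keep expectation out of the answers. An open invitation to consult the coach while answering is a way around that protection. Neither document supplies a neutral script, a separate contact for survey questions, or a record of when such help was given. Section 6.1.2 counts coach interactions over the first 12 weeks as engagement, but that count neither separates questions about outcome items nor runs to month 6.

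At stake is whether a between-arm difference in reported pain interference can be read as an effect of the programme content.

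**Working it through.** The plan gives no figure for coach contacts or reporting bias, so there is none to reproduce. The check is mainly a comparison of passages.

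**1. Does the coach know the arm?** No passage says so. It follows from the role: reinforcing CBT skills or discussing education content requires knowing which content the participant has. The trial is open-label and no passage blinds coaches. Knowledge of the arm is therefore very probable, but inferred.

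**2. Is coach talk about outcome items limited?** Not in either document. Section 7.3 refers to a Health Coach Protocol that is not among the documents, so a limit could stand there.

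**3. Does this reach the month-6 endpoint?**
- Guidance: the explicit sentence covers month 3. At month 6 the coach is available on request, with nothing excluding questionnaire questions.
- Reminders: section 6.4 covers all time points. A reminder mainly affects whether an answer is given; guidance is the more direct route to a changed answer.
- Model: the SAP fits a linear mixed model to the repeated measures, so month-3 scores enter it. If time is fitted as a trend, they bear directly on the 6-month contrast. If time is categorical, they bear on it mainly through participants whose month-6 score is missing. The SAP does not say which.

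**4. What must be true for the contrast to be biased?** Let p be the share of an arm's analysed participants who receive coach guidance on the items, and s the average shift in their score. The bias in the between-arm contrast is

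B = p(cCBT) × s(cCBT) − p(Education) × s(Education).

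If guidance is equally common and shifts scores equally in both arms, B = 0. A bias needs the coaches' influence to differ by arm, through what they say or how often they are asked. The documents give neither p nor s.

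**5. Sensitivity illustration, not an estimate.** Inputs: N = 350, 1:1 allocation and 15% attrition (protocol 9.2 and SAP Sample Size Calculation), giving 350 × 0.85 / 2 = 148.75 per arm. Two-sided alpha of 0.05 is assumed for the primary test; the protocol states that level only for the interaction tests (9.4.6). Using a simple two-group comparison in SD units with no true effect:

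SE = √(2 / 148.75) = 0.116

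P(reject) = Φ(−1.96 − B/SE) + 1 − Φ(1.96 − B/SE)

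| Assumed B (SD) | P(reject) | Shift needed if 20% of one arm is affected, none in the other | Same, 30% |
|---|---|---|---|
| 0 | 5.0% | – | – |
| 0.05 | 7.2% | 0.05/0.20 = 0.25 SD | 0.05/0.30 = 0.17 SD |
| 0.10 | 13.9% | 0.10/0.20 = 0.50 SD | 0.10/0.30 = 0.33 SD |
| 0.20 | 40.7% | 0.20/0.20 = 1.00 SD | 0.20/0.30 = 0.67 SD |

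The 20% and 30% shares are assumptions. A small differential bias would matter, but the larger rows need shifts from a brief exchange that approach or exceed the 0.37 SD the trial is sized for.

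**The case against.** The strongest reply is that participants complete the surveys alone through an online link, and that answering an occasional question is not an interview. Coach support is planned for both arms on the same platform (section 4.3), so influence common to both cancels. Coaches also aid retention: stakeholders called the coach important and necessary (section 4.2), and losing coach reminders could cost data. All of this stands. It limits the size of the concern but does not supply the missing limit on what coaches may say.

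Several stronger readings are tempting, and the documents do not support them:

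- *Coaches take participants through the questionnaire.* The text offers help only to those with questions.
- *Each arm has its own coaches.* Section 4.1 speaks only of one of the health coaches, and section 5.5 mentions coach assignment before access to the app, where randomisation takes place. Coaches may serve both arms.
- *Section 6.3 promises to keep coaches away from data collection.* The phrase "separates data collection, monitoring, and analysis from the day-to-day implementation of the study interventions" describes the division of duties between two principal investigators, meant to limit investigator bias. It makes no promise about coaches.
- *Sections 6.4 and 7.3 contradict each other on who chases missing data.* Section 7.3 says "every possible effort will be made by study site personnel to contact the subject" when a follow-up is not completed, and also gives coaches outreach to participants who stop reporting. Early coach reminders followed by site escalation is a consistent reading. The sequence is unstated rather than contradictory.
- *Extra coach contacts fall outside the planned dose.* The synopsis allows contact more often than weekly when requested or needed.

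**Conclusion.** The point holds as a gap in a safeguard. A coach who very probably knows the arm may advise on the self-reported primary questionnaire, explicitly at month 3 and by continued availability at month 6, with no stated limit on content. This weakens the expectation-bias protection in section 6.3 but does not undo it.

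The size is unknown. A reader might insert guesses, such as 20–30% of participants affected by 0.2–0.3 SD in one arm only, and obtain 0.20 × 0.2 = 0.04 to 0.30 × 0.3 = 0.09 SD, or 11–24% of 0.37 SD. The documents support neither input, nor the premise that the whole shift falls in one arm. No figure for the bias should be reported.

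The conclusion rests on two assumptions: that coaches know the arm, and that the Health Coach Protocol contains no restriction of its own. Bias in the treatment contrast is plausible but not shown. This is a cheap improvement, not a flaw that threatens the trial.

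**What to change.** 1. **Section 4.1 (T1, with the same wording for T2 and T3) and section 6.4.** Replace the invitation to ask the coach with a rule that questions about understanding or answering an outcome questionnaire go to existing study staff who do not deliver the intervention. These staff should be kept unaware of the arm where feasible and should use a fixed neutral script.
2. **Section 6.4.** Let coaches go on sending completion reminders, scripted and without discussion of item content.
3. **Sections 2.3.3 and 8.3.** Leave the coaches' suicide-risk, deterioration and nonresponse monitoring unchanged. A blanket bar on discussing symptoms would conflict with it.
4. **Sections 6.4 and 7.3.** State how coach reminders and site-personnel contact attempts fit together, for instance which comes first and when responsibility passes.

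**Cost.** Protocol and coach-manual wording, a short script, and a named contact among existing staff. Participants may be slightly less ready to put a question to someone other than their coach. Keeping reminders with the coaches avoids the larger retention risk of moving all outreach to an unfamiliar contact.

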**Primary Outcome.**

Aim 1 of this study is to compare the effectiveness of two mobile phone-delivered programs—cCBT versus pain and SCD education (m-Education)—for reducing SCD pain symptoms (i.e. pain interference). The secondary outcome we expect to change in this study is daily pain intensity. As mentioned above, patients will track pain symptoms using an electronic diary where they will be prompted to complete a symptoms survey once a day. Participants will be encouraged to enter their pain symptoms daily. They will receive reminders to keep entering daily data at each time point (T0, T1, T2, T3). Participants will have the option to snooze the prompt until a more convenient time. For the electronic diary, some format of the following will be administered:

Daily

- Using any number from 0 to 10, where 0 is no pain and 10 is the worst pain imaginable, what is your pain level today?
- Did you take opioid medications today?
- Which one of the following emojis best represents your mood today?

Weekly

- Using any number from 0 to 10, where 0 is no pain and 10 is the worst pain imaginable, what is your pain level today?
- Did you take opiate medications today?
- Compared to what you used yesterday, is the amount of opiate meds you took today less than yesterday, the same as yesterday, or more than yesterday?
- Did you take non-opiate medications today?
- This past week, how often have you been bothered by little interest or pleasure in doing things?
- This past week, how often have you been bothered by feeling down, depressed, or irritable?
- This past week, how often have you been bothered by feeling nervous, anxious, or on edge?
- This past week, how often have you been bothered by not being able to stop or control worry?

**Secondary Outcome Measures.** Aim 2 of this study is to assess whether baseline depression symptoms moderate the effect of intervention on pain outcomes. To achieve this, patients will be asked to complete the PROMIS Pain Interference Scale at baseline, 3 months, 6 months, and 12 months; PROMIS is a validated questionnaire asking a patient how most day-to-day function is altered by pain. In addition, to assess changes in quality of life and emotional distress, participants will complete the following tests at baseline, 3 months, 6 months, and 12 months: Adult Sickle Cell Quality of Life Measurement Information System (ASCQ-ME); Emotional Functioning and Social Impact scales; the Patient Health Questionnaire (PHQ9), a 9-item measure of depressive symptoms; and the Generalized Anxiety Disorder Scale (GAD-7). Lastly, to assess changes in use of prescribed opioids, participants will complete the Current Opioid Misuse Measure (COMM) at baseline and 12 month follow-up. See **Table 4**.

**Medical Outcomes (PCORnet).**

For patients recruited at one of the five clinical sites, we will evaluate objectively measured opioid medication refills and emergency department visits or hospitalizations for pain crisis. We will be working in collaboration with PCORnet to collect data retrospectively (from the past 12 months) and prospectively (12 months from date of enrollment) from patient medical records. These data will allow us to track medications including opioid pain medication prescriptions and refills, and health care utilization (i.e., emergency department visits and

hospitalizations), as well as lab values (e.g., hemoglobin level) and clinical outcomes (e.g., end-organ damage score). For the patients recruited from our community partner organizations or online who are not affiliated with a participating clinical center, we will only acquire or evaluate their medical records for the purpose of confirming their sickle cell diagnosis.

**Process evaluation measures.** For the intervention to be effective, patients must use the program and acquire coping skills or knowledge about pain and SCD that will help them manage their physical health (e.g., nutrition/exercise), emotional distress, and physiological response to stressors, all factors contributing to pain. As they progress through the intervention, participants will complete elements of the Coping Strategies Questionnaire for sickle cell disease (CSQ) and the Sickle Cell Self-Efficacy Scale (SCSES) shown in **Figure 6**.

1) How sure are you that you can do something to cut down on most of the pain you have when having a pain episode?	Not at all sure	Not sure	Neither	Sure	Very Sure
2) How sure are you that you can keep doing most of the things you do day-to-day?	Not at all sure	Not sure	Neither	Sure	Very Sure
3) How sure are you that you can keep sickle cell disease pain from interfering with your sleep?	Not at all sure	Not sure	Neither	Sure	Very Sure
4) How sure are you that you can reduce your sickle cell disease pain by using methods other than taking extra medication?	Not at all sure	Not sure	Neither	Sure	Very Sure
5) How sure are you that you can control how often or when you get tired?	Not at all sure	Not sure	Neither	Sure	Very Sure
6) How sure are you that you can do something to help yourself feel better if you are feeling sad or blue?	Not at all sure	Not sure	Neither	Sure	Very Sure
7) As compared with other people with sickle cell disease, how sure are you that you can manage your life from day-to-day?	Not at all sure	Not sure	Neither	Sure	Very Sure
8) How sure are you that you can manage your sickle cell disease symptoms so that you can do the things you enjoy doing?	Not at all sure	Not sure	Neither	Sure	Very Sure
9) How sure are you that you can deal with the frustration of having sickle cell disease?	Not at all sure	Not sure	Neither	Sure	Very Sure

**Figure 6** - The nine-question Sickle Cell Self-Efficacy Scale (SCSES)

**Qualitative Interviews.** Lastly, to further understand which intervention works best for whom and when, the lived experience of patients in the trial, and differences in perceptions between depression subgroups, we will do a series of qualitative interviews with patients enrolled in both arms of the study, at three time points in the study—at baseline, in order to assess prior patient experience with SCD and treatment for SCD, and their attitudes toward the intervention at the outset; at 3 months when the initial intervention concludes in order to assess their experience with and opinions on the intervention; and at 6-12 months to assess long-term impact of the intervention. At each time point, Qual EASE will select and interview 24 patients in each treatment group, stratified by high or low depression scores, for a total of 48 interviews (i.e., 12 cCBT patients with PHQ  $\leq$ 10, 12 cCBT patients with PHQ  $>$ 10, 12 m-Education patients with PHQ  $\leq$ 10, 12 m-Education patients with PHQ  $>$ 10). This will allow us to qualitatively compare the experiences of patients with differing depression levels, and to explore quantitative findings with regards to intervention efficacy in patients with differing levels of depression severity. Patient sample size has been selected to allow for high likelihood of our reaching thematic saturation regarding patient experience.

